- **The Evaluable Population (EP)** consists of all enrolled patients who, completed at least 1 cycle of poziotinib treatment, and have baseline and at least 1 post-baseline tumor response evaluation using RECIST, version 1.1 (and/or RANO for **Cohort 4**) or progressed prior to any post-baseline image evaluation. All efficacy analyses will be done using the **Evaluable Population**.
- The **Safety Analysis Population (SAF)** includes all enrolled patients who received at least 1 dose of poziotinib. All demographics, Baseline characteristics, and safety data will be analyzed using the **SAF** population.

Safety and Tolerability:

The following variables will be summarized and analyzed descriptively for each cohort: number of completed cycles, relative dose intensity, number and percentages of patients with TEAEs, SAEs, TEAEs leading to study drug discontinuation, TEAEs related to the study drug; and the severity of TEAEs based on CTCAE, Version 5.0.

Protocol Version/Date: Amendment 1/ 20 May 2021

Study Design Diagram

SCHEDULE OF ASSESSMENTS AND PROCEDURES

Assessment	Screening (30 days prior to Day 1, Cycle 1)	Treatment Period ^a (Each Cycle=28 [±3] Days)						End of Treatment (EOT) Visit	Long-Term Follow-up Every 3 months for 2 years
		Cycle 1 ^b			Cycle 2		Cycle 3+		
	Day -30 to Day 1	Day 1	Day 8±1	Day 15±3	Day 1	Day 8±1	Day 1	30 (±5) Days After Last Dose ^c	
Informed Consent	x								
Relevant Medical History	x								
Demographic Data	x								
Height and Weight	x	x			x		x	x	
Physical Examination ^d	x	x	x	x	x		x	x	
Vital signs	x	x	x	x	x		x	x	
ECOG Performance Status	x	x			x		x	x	
Pregnancy Test ^e	x	x			x		x	x	
Tumor Assessment	x ^f				x		x	x	
Tumor Histopathology Report ^g	x								
CBC with 5-part differential and platelets ^h	x	x	x		x	x	x	x	
Serum Chemistry ⁱ	x	x ^l			x		x	x	
Electrocardiogram (ECG) ^j	x	x	x						
Echocardiogram or MUGA Scan ^k	x								
Tissue Samples ^l	x							x	
Plasma Samples ^m	x				x		x ^l	x	
Whole Blood Sample ⁿ	x								
PK Samples ^o		x	x		x				
Dispense Poziotinib and Loperamide ^p		x			x		x		
Adverse Event Assessment	x ^q	x	x ^r	x	x	x ^r	x	x	x
Dispense and Collect Patient Diary		x	x		x	x	x	x	
Concomitant Medications review	x	x	x	x	x	x	x	x	
Telephone Contact ^s									x

- a) Each treatment cycle is 28 days with a visit window of ± 3 day. If a visit is delayed during 1 Cycle, the subsequent schedules will be delayed sequentially.
- b) Patients will be contacted by telephone on Days 3-8 and on Day 22 for assessment of adverse events.
- c) An **End-of-Treatment Visit** will be performed 30 (±5) days after the last dose of poziotinib. An End of Study page will be recorded at that time.
- d) A complete physical examination is required at **Screening**, **Day 1** of each Cycle, at Days 8 and 15 of Cycle 1, and at the **End-of-Treatment Visit**. Symptom-directed exams if clinically indicated are required at other visits.
- e) Pregnancy test (β-HCG) in women of child-bearing potential. Blood pregnancy test is required at **Screening**. Urine pregnancy test is required on Day 1 of each Cycle starting from **Cycle 2** and at **Cycle 1, Day 1**, if Screening pregnancy test was more than 7 days prior to **Day 1**. Urine pregnancy test also required at **End-of-Treatment Visit**.

- f) The **Screening** tumor assessment for patient eligibility will be based on scans performed within 30 days before the patient signed the ICF. Either CT, PET/CT, or MRI scans should be performed for non-brain organs and brain MRI scans should be performed locally per standard of care before the patient signed the ICF. **Baseline** tumor assessment (CT, PET/CT or MRI for non-brain and brain MRI) will be performed within 14 days prior to **Cycle 1, Day 1** and additional assessments will be made at 4 weeks (**Cycle 2, Day 1** [up to **Cycle 2, Day 7**]), at 8 weeks (**Cycle 3, Day 1** [up to **Cycle 3, Day 7**, with at least 28 days from previous tumor assessment]), and then every 8 weeks (± 7 days) thereafter until disease progression, death, intolerable adverse events (AEs), or other protocol-specified reasons for patient withdrawal.
- g) Tumor histopathology report (from local pathologist) and molecular test report for mutation diagnosis.
- h) Complete blood count (CBC), including white blood cells with 5-part differential, hemoglobin, and platelets, is to be obtained within 7 days prior to poziotinib administration on **Day 1** of each cycle, at which time, the patient's absolute neutrophil count $\geq 1.0 \times 10^9/L$ and platelet count $\geq 75 \times 10^9/L$ before administering the next dose of poziotinib. In addition, a CBC is to be performed on **Day 8** of **Cycles 1 and 2**.
- i) Blood for chemistry is to be collected within 7 days prior to poziotinib administration on **Day 1** of each Cycle.
- j) ECGs will be performed at screening. At select study centers, up to 25 patients may be specifically consented for ECG as defined below:
Schedule: A local 12-lead ECG will be obtained just before each PK blood sample on both Day 1 and Day 8. If the patient has interrupted continuous poziotinib dosing, clear dosing documentation must be done in order to assess suitability of further PK sampling and ECG recording.
- k) Cardiac ejection fraction may be evaluated at **Screening** in patients who are considered at high risk of cardiac disease, as determined by the Investigator, using echocardiogram or multi-gated acquisition (MUGA) scan. The investigator can order subsequent tests based on patient standard of care as determined by the Investigator.
- l) Tumor genotyping report from local lab is required to confirm patient mutation eligibility. Tissue sample (archival or fresh biopsy), if available, should be retained for retrospective analysis by FoundationOne CDx test. Collecting a tissue sample at progression is optional but is highly encouraged.
- m) Plasma samples will be required at **Screening** and optional on the day of each on-study imaging session, beginning at the 4-week imaging session, once every 8 weeks with imaging scan and when the patient progresses for biomarker analysis. Guardant's 360 or FoundationACT assays will be used, Plasma sample collection and storage will follow vendors' standard procedures as described in the vendors' Laboratory Manual.
- n) Whole blood samples will be drawn at **Screening** for pharmacogenomic analysis.
- o) At select study centers, up to 25 patients may be specifically consented for intensive PK sampling as defined below:
Schedule: Intensive PK blood sampling will be at pre-dose and 2, 4, 8, 12, and 24 hours post-dose on **Cycle 1, Day 1** and on **Cycle 1, Day 8 (± 3 days)**. The 12-hour and 24-hour PK samples must be collected prior to the second daily dose. If the patient has interrupted continuous poziotinib dosing, clear dosing documentation must be done in order to assess suitability of further PK sampling and ECG recording. In addition, if a patient presents with a potentially drug-related Grade ≥ 3 AE, a PK sample should be collected as soon as possible, if feasible, following the onset of the AE in order to characterize the PK. Documentation of last dose timing prior to the event is required.
- p) Poziotinib and loperamide will be dispensed on **Day 1** of each cycle. Patients will take poziotinib orally twice daily with food and a glass of water at approximately the same times each day. Loperamide will be given prophylactically for diarrhea as follows: 4 mg twice daily (bid) to three times daily (tid or according to treating physician's instruction).
- q) Adverse events will be assessed using National Cancer Institute Common Terminology Criteria for Adverse Events (CTCAE, version 5.0) and during **Screening** only study-related SAEs to be recorded.
- r) Weekly calls to patients will be conducted during the Days 3 to 8 of each cycle for the first 2 cycles as a follow up of expected adverse events.
- s) Patients who have consented will be contacted by phone (or email or letter if specifically requested) every 3 months, for up to 2 years after patient's first dose of poziotinib, for survival assessment.

Poziotinib Dose Modification Recommendations

If needed, the initial dose (8 mg BID) may be reduced by 2 mg for each dose (ie 12 mg per day divided into 6 mg BID doses) at the Investigator’s discretion and the Sponsor should be notified. If further dose reduction is required, the next dose should be reduced by a total of 2 mg/day (ie 10 mg per day divided into a 6 mg and 4 mg dose per day) and the Sponsor should be notified. Any further reductions in dose must be discussed a priori with the Sponsor’s Medical Monitor and approval is required.

No dose reductions below 8 mg total dose/day are allowed.

Poziotinib Dose Modification Recommendations

Related Adverse Event	Grade	Occurrence	
		1	Each Additional Occurrence
Diarrhea	Grade ≥3 (Despite adequate anti-diarrhea management)	Stop poziotinib treatment until AE Grade ≤1 and then continue treatment at the same dose ^a or Reduce Poziotinib Dose by 2 mg/dose	Reduce Poziotinib Dose by ~1 mg/dose
	Grade ≥2 for ≥48 hours (Despite adequate diarrhea management)		
Fatigue	Grade ≥3		
Mucositis/ Stomatitis	Grade ≥3 (Despite adequate management)		
Nausea and/or Vomiting	Grade ≥3 (Despite adequate anti-emetics)		
	Grade ≥2 for ≥48 hours (Despite adequate anti-emetics)		
Rash	Any Grade	Refer to Appendix 4 .	
LVEF Dysfunction	Grade ≥3	Discontinue Treatment	

a) Supportive medications, including early steroid use, should be considered even in the presence of low-grade “on-target” toxicity (eg, rash, diarrhea) ([Appendix 4](#)).

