
Duration of Study: The total duration of the study will be approximately four (4) years, including enrollment and follow-up. The duration of study participation for each patient includes the following:
 
 Screening Period: Up to 30 days Treatment Period: 28 days per cycle for up to 24 months of treatment or until death, intolerable adverse events, progressive disease or other protocol-specified reasons for patient withdrawal End-of-Treatment Visit: 30 (±5) days after the last dose of poziotinib Long-Term Follow-up: After treatment period discontinuation, patients who have consented will be contacted every 3 months, for up to 2 years after patient’s first dose of poziotinib, for survival assessment. 	

Patient Replacement Strategy: Patients not efficacy evaluable i.e. not completed at least 1 cycle of poziotinib treatment and have baseline and at least 1 post-baseline tumor response evaluation using RECIST, version 1.1 (and/or RANO for Cohort 4) will be replaced unless they have discontinued from treatment or from the study due to disease progression or probable disease progression (eg. clinical progression, initiation of new therapy) or due to toxicity.
	

Study Design and Methodology
 
This is a Phase 2 multicenter, open-label study to evaluate the efficacy and safety of poziotinib in patients with EGFR or HER2 mutation-positive malignant solid tumors.
	

The study is a basket trial with five cohorts. The primary analysis will be conducted for each cohort separately. The five cohorts are:

- **Cohort 1:** Patients that have HER2-positive or HER2-negative, breast cancer with HER2 activating mutations (see **Table A**) (N=30) (See **Inclusion Criteria #4**)
- **Cohort 2:** Patients that have colorectal cancer with HER2 activating mutations (see **Table A**) (N=30)
- **Cohort 3:** Patients that have solid tumors (except NSCLC, breast cancer, or colorectal cancer) with HER2 activating mutations (see **Table A**) (N=30)
- **Cohort 4:** Patients that have GBM with EGFR activating mutations (see **Table A**) (N=30)
- **Cohort 5:** Patients that have solid tumors (except NSCLC or GBM) with EGFR activating mutations (see **Table A**) (N=30)

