4.3 Patient Discontinuation/Withdrawal Criteria

Patients can withdraw from participation in this study at any time, for any reason, specified or unspecified, and without prejudice.

All treated patients must be withdrawn from the study due to the following reasons:

- Development of an adverse event (AE) that interferes with the patient's participation
- Initiation of non-protocol therapy
- Development of progressive disease (PD)
- Patient withdrawal of informed consent
- Delay of poziotinib administration for >28 days since last study drug administration
- Investigator decision
- Sponsor decision

- Lost to follow-up
- Pregnancy
- Death

The reason for the patient discontinuing study treatment or terminating from the study must be recorded on the case report form (CRF). Patients who discontinue treatment or who are withdrawn from treatment will return for an End-of-Treatment Visit 30 (± 5) days after the last dose of poziotinib or prior to beginning a new treatment, whichever is first. If death is recorded as the reason for study discontinuation, the cause of death should be recorded on the CRF. Patients not efficacy evaluable i.e. not completed at least 1 cycle of poziotinib treatment and have baseline and at least 1 post-baseline tumor response evaluation using RECIST, version 1.1 (and/or RANO for **Cohort 4**) will be replaced unless they have discontinued from treatment or from the study due to disease progression or probable disease progression (eg. clinical progression, initiation of new therapy) or due to toxicity.

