8.1 Sample Size

The statistical analysis of each cohort will be performed separately. A total of 30 patients in each cohort will be enrolled using Simon's two-stage design. The optimal two-stage design to test the null hypothesis that $p \leq 0.050$ versus the alternative that $p \geq 0.250$ has an expected sample size of 16.76 and a probability of early termination of 0.630. If the drug is not effective, there is a 0.049 probability of concluding that it is (the target for this value was 0.050). If the drug is effective, there is a 0.098 probability of concluding that it is not (the target for this value was 0.100). For each cohort, 9 patients will be evaluated in the first stage; the cohort will be terminated if 0 respond. If the cohort goes on to the second stage, a total of 30 patients will be studied. If the total number responding is less than or equal to 3, the cohort is closed.

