8.3 Analysis Populations

The following analysis populations will be defined.

- **The Evaluable Population (EP)** consists of all enrolled patients who completed at least 6 weeks of poziotinib treatment, and have baseline and at least 1 post-baseline tumor response evaluation using RECIST, version 1.1 (and/or RANO for Cohort 4) or

progressed prior to any post-baseline image evaluation. All efficacy analyses will also be done using the Evaluable Population.

- The **Safety Analysis Population (SAF)** includes all enrolled patients who received at least 1 dose of poziotinib. All demographics, Baseline characteristics, and safety data will be analyzed using the SAF population.

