8.4 General Statistical Methods

The Sponsor's Biostatistics and Data Management group will be responsible for data management and statistical analysis of this study. All statistical analyses will be performed using SAS for Windows (Version 9.4 or higher). Patient data listings and tabular presentations of results will be provided. Further details of the criteria and conduct of the statistical analyses will be included in the SAP for this study.

8.5 Efficacy Analysis:

The primary efficacy variable ORR is the proportion of patients with confirmed Complete Response (CR) and Partial Response (PR) recorded from the start of the first dose of poziotinib to the end of study and will be analyzed descriptively along with the 95% CI for each cohort. The determination of ORR will be based upon an assessment of the local radiological review by the respective Principal Investigator using RECIST version 1.1 and/or RANO criteria (for GBM). Confirmatory assessments must be completed by the Investigator 4 weeks \pm 3 days after the first assessment of CR or PR and only confirmed CR/PR can be deemed as CR/PR.

The secondary endpoints are DCR and DoR, DCR is the proportion of patients with best response of CR, PR, and Stable Disease (SD) from the first dose of poziotinib to the end of study; and DoR is the time from the date that measurement criteria are first met for CR or PR (whichever status is recorded first) until the first subsequent date that progressive disease or death is documented.

Exploratory endpoints are OS and PFS. OS is the time from the treatment start date to the date of death during the study and PFS is the time from the treatment start date to the date of documented disease progression or death during the study.

DCR, DoR, OS, and PFS will be analyzed using descriptive statistics, for each cohort, and with 95% CI for DCR and Kaplan-Meier plot for DoR, OS, and PFS.

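### Some deaths before the first scan fall outside the only efficacy population, and those of other or unknown cause are also replaced, so OS and PFS lose early events and ORR loses certain non-responders

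*Combined protocol and SAP*

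**What the plan says.** **Replacement (Synopsis, Patient Replacement Strategy; Section 4.3).** Patients who are not efficacy evaluable "will be replaced unless they have discontinued from treatment or from the study due to disease progression or probable disease progression". The sentence goes on to give clinical progression and new therapy as examples of probable progression, and adds toxicity as a further exemption. Death is not mentioned. Section 4.3 lists death as its own withdrawal reason, apart from progression and adverse events, and adds: "If death is recorded as the reason for study discontinuation, the cause of death should be recorded on the CRF".

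**Evaluable Population (Synopsis, Analysis Populations; Section 8.3).** Entry requires a minimum time on treatment (one cycle in the Synopsis, 6 weeks in 8.3) and a baseline and at least one post-baseline tumor evaluation. The only route in without a scan is for patients who "or progressed prior to any post-baseline image evaluation", where the subject is progression and not death.

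**Use of the populations.** Section 8.3 says: "All efficacy analyses will also be done using the Evaluable Population". The Safety Analysis Population, which is all dosed patients, is assigned only to demographics, baseline characteristics and safety.

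**Endpoints (Section 8.5).** "OS is the time from the treatment start date to the date of death during the study". PFS starts at the same point and counts progression or death.

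**Stage counts.** The study design text says stage 1 will enroll 9 patients per cohort. Section 8.1 says 9 will be evaluated. Neither names the population for the 9 and the 30.

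**The concern.** The two rules have different exits. The replacement rule spares progression, probable progression and toxicity. The Evaluable Population spares progression only. Neither spares death as such. Whether a patient is analysed for survival can thus depend on having died early and on the cause assigned to the death. That is selection on the outcome. OS in particular needs no scan, so evaluability for response is no reason to leave a dosed patient out of it.

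For ORR, a patient who dies before the Week 4 scan cannot have a confirmed response. Replacing that patient exchanges a certain non-responder for someone who may respond. ORR is the primary endpoint and drives the stop or continue decision in each of five cohorts, so this matters more than the effect on the exploratory survival curves.

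**Working it through.** **1. What happens to each kind of death before the first post-baseline scan**

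| Cause assigned | Replaced? | In Evaluable Population? |
|---|---|---|
| Progression, recorded as such | No | Yes, through the progression clause |
| Probable progression | No | Undefined: the clause says only progressed |
| Toxicity | No | No |
| Other or unknown | Yes | No |

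The last two rows are lost from ORR, DCR, PFS and OS. Only the last row affects replacement. Read literally, the 6-week minimum in 8.3 also drops a patient who is scanned at Week 4 and dies without progression before week 6.

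**2. The plan's own design figures**

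Inputs from Section 8.1: null rate 0.05, alternative 0.25, stop at 0 of 9, close at 3 or fewer of 30.

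- Early termination: 0.95^9 = 0.630.
- Expected size: 9 + (1 − 0.6302) × 21 = 16.76.
- Pass probability: sum over x = 1 to 9 of b(x; 9, p) × P(Y ≥ max(0, 4 − x)), with Y binomial(21, p). At p = 0.05 this is 0.0489. At p = 0.25 it is 0.9019, so the type II error is 0.098.

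All agree with the plan: "If the drug is not effective, there is a 0.049 probability of concluding that it is" and "there is a 0.098 probability of concluding that it is not".

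**3. Effect of replacement on the pass probability**

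Let d be the share of dosed patients who die before a scan and are replaced, all of them non-responders. A true rate of 0.05 in all dosed patients becomes 0.05 / (1 − d) in those counted. The documents give no d, so a range is assumed, and the 9 and 30 are assumed to exclude replaced patients.

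| d | Rate counted | Early termination | Pass probability |
|---|---|---|---|
| 0 | 0.0500 | 0.630 | 0.049 |
| 1% | 0.0505 | 0.627 | 0.050 |
| 2.5% | 0.0513 | 0.623 | 0.053 |
| 5% | 0.0526 | 0.615 | 0.057 |
| 10% | 0.0556 | 0.598 | 0.067 |

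At the smallest passing count, 4/30 = 13.3% (exact 95% CI 3.8% to 30.7%). Restoring three replaced deaths gives 4/33 = 12.1% (3.4% to 28.2%).

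**4. Effect on median OS**

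Assume exponential OS with a true median of 6 months. Deaths by Day 28 (0.92 months): P = 1 − 2^(−0.92/6) = 10.1%. If a fraction f of these is left out, the observed median t solves S(t) = 0.5 × (1 − f × P), so t = −6 × log2[0.5 × (1 − f × P)].

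| f | Share of dosed patients left out | Median, months | Change |
|---|---|---|---|
| 10% | 1.0% | 6.09 | +1.5% |
| 25% | 2.5% | 6.22 | +3.7% |
| 50% | 5.0% | 6.45 | +7% |
| 100% | 10.1% | 6.92 | +15% |

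The last row is a ceiling, not an expected value. Deaths from toxicity belong in f here but not in d above.

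**The case against.** A reader might infer that every early death without recorded progression is replaced. The documents do not support that. The exemption extends to probable progression and to toxicity, and the required cause of death lets a death be assigned to either. Only deaths of other or unknown cause are clearly replaced.

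A reader might also take the 15% longer median as the likely bias. It requires every early death to be left out, whereas the Evaluable Population keeps patients who progressed before a scan. The rule does not reach that figure if any early death is due to progression. A constant hazard from Day 1 is also doubtful in patients enrolled with ECOG 0 or 1 and without other serious illness. A tenth to a quarter of early deaths lost would move the median by only 1.5% to 3.7%, and the pass probability, if all of those deaths were replaced, to 0.050 to 0.053.

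Nor is it stated that the Simon counts are taken in the Evaluable Population. Evaluating 9 patients, together with a replacement rule, points that way. Enrolling 9 points the other way. The type I error result is conditional on the first reading.

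Finally, OS and PFS are exploratory and descriptive, and a separate SAP is still due before database lock. That limits the weight of the point but does not answer it. The Synopsis and Section 8.3 already fix the population for efficacy, and although 8.3 says the analyses will *also* use it, no other efficacy population is defined.

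**Conclusion.** The gap is real but narrow. As written, a death before the first scan that is not attributed to progression, probable progression or toxicity is both replaced and left out of all efficacy analyses. A toxic death before a scan is left out without being replaced. The status of a probable-progression death is undefined. The direction is certain: each patient left out is an early OS and PFS event and cannot be a confirmed responder.

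The size is not known, because the documents give no early-death rate. On the assumptions shown, plausible partial losses lengthen a 6-month median OS by about 1.5% to 7%. If the stage counts follow the replacement rule, replaced deaths among 1% to 10% of dosed patients put the pass probability at 0.050 to 0.067 for a true all-treated ORR of 5%. The stated 0.049 would then no longer describe all treated patients. The point should be corrected, but it does not by itself undermine the design.

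**What to change.** 1. Analyse OS and PFS in the Safety Analysis Population, from first dose.
2. Add death from any cause to the exemptions from replacement, in the Synopsis and Section 4.3. In the Evaluable Population definition (Synopsis and 8.3), let the clause cover patients who progressed or died before any post-baseline image, whatever their time on treatment. Count these patients as non-responders in ORR and in the 9 and 30.
3. Treat patients who stop for toxicity or probable progression before a scan, and so are not replaced, in the same way: in the Evaluable Population, as non-responders. The replacement rule and the population then agree.

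This needs wording changes in the protocol and the forthcoming SAP. It needs no new data, since the Safety Analysis Population already exists and deaths are already recorded. The cost is that ORR, PFS and OS may read slightly less favourably. Patients who withdraw or are lost before a scan would still be replaced, so the stage counts would come closer to all treated patients without being identical to them.
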